Written informed consent to obtain and use clinical data and specimens will be requested by the research staff, using paper or electronic (eConsent via REDCap survey format on computer or tablet) consents. If the participant is seen in person, the default will be paper consents. The participant will be given the opportunity to read the consent before the study coordinator goes over it with them. The study coordinator will introduce him or herself to the potential participant during the course of a normal outpatient clinic visit, describe the study in further detail including the possible discomforts of the procedure(s), the purposes for which the samples are being taken, and that s/he will not personally benefit from the results. Any questions that the patient might have will be answered by the study staff as appropriate. This process will be conducted in a closed room within the clinic to ensure a proper, private environment. If they agree to participate, the study coordinator will ask the patient to sign the standard participation consent and a HIPAA form.

Once the participant has the informed consent open on a computer or tablet, they are able to scroll through (using mouse or finger) and read the document in its entirety, just as they would an article on a website. The study coordinator will guide the participant through the consent, asking open-ended questions to assess their comprehension of the study procedures. As the participant finishes reading sections of the document that require initialing or signature to provide consent for specific procedures, they are given the ability to do so by clicking on a link stating "add signature." Each of these links provides verbiage identical to the paper consent form indicating the procedures for which they are being consented. These initials and signatures are completed by using their finger (tablet) or the mouse (computer) and accepting the changes by clicking "save signature." Only the portions of the document that require the initials or signature of the participant will be provided to the participant, ensuring that they will not sign, initial, or date the improper portion of the document (e.g. – signing on the line for the person obtaining consent). The study coordinator will then be allowed to print their name, sign and date the form independent of the participant. The "submit" button is then pressed at the bottom of the screen by the study coordinator which then automatically opens the HIPAA document for the same review and signature/initialing process as above. Just as for paper copy consenting above, the eConsent process will be conducted in a closed room within the clinic to ensure a proper, private environment, and the study coordinator will conduct the eConsent process over the phone with the participant. In this event, the participant will be sent an electronic copy via email before the consent call, so that they can read the documents before the researcher goes over it. All participants will receive copies of the appropriate consent forms and HIPAA notice.

Given the complexity of SLE and the overall study goal to provide modeling and reinforcement by peers to other African American women with lupus (mentees) to encourage mentees to engage in activities that promote the learning of disease self-management skills and support the mentees' practice of these learned skills, every attempt will be made to ensure that the study/mentorship does not negatively impact the mentee. To address this potential concern the following approach will be implemented:

- 1. Upon enrollment, peer mentors will receive training, prior to working with mentees.
- 2. Mentors will be given a written manual presenting all the material in detail for their ongoing reference.
- 3. Mentors will be given parameters for their roles and instructed on how to handle potential issues that may arise (e.g. not providing clinical advice) along with role-playing.
- 4. After the initial training, peer mentors will continue to meet with the PI weekly to identify challenges and reinforce the guidelines for peer mentors. During these meetings, the PI will also monitor mentors' comfort with interactions and their mentee load. If mentors express discomfort and/or feeling overwhelmed, mentees will be reassigned and/or redistributed.
- 5. Bi-weekly surveys to mentees and PI meetings with mentors will be used to track participant satisfaction with the peer mentoring process.

Additional protections against potential risks include the following:

- 1. Psychological Distress: Because we will be administering a questionnaire that measures the presence of depression, we will take several steps to ensure the safety of research participants. RAs will be trained by the PI to identify patients who meet criteria for depression on the PHQ-9. Participants who screen positive for depression will be assessed by a clinician before leaving their study visit to ensure their well-being and verbally instructed to seek care from their PCP. If deemed appropriate, they will also be given the Suicide Prevention National Hotline, [name], and told to call if they experience acute worsening of symptoms before they can be seen by their PCP.
- 2. Administration of Research Questionnaires: Some participants might be offended by detailed questions about emotional or physical health status and impairment. All participants will be informed at the outset that they may terminate participation at any point. Past research suggests that data collection using these measures can be conducted without undue psychological distress or exacerbation of symptoms among study participants.
- 3. Unknown risks: Participation in research may have other unknown risks. The researchers will advise participants if they learn of emerging information that might alter participants' decisions to participate.

In an effort to manage any high-risk aspects of the proposed work, potential mentees will be screened for depression and anxiety prior to pairing and mentors will be provided with summary sheets for each of their assigned mentees, to ensure that we are not putting mentors in a situation where they have to counsel those with serious mental health concerns (i.e., not expecting them to manage clinical depression, suicidality, etc.). Additionally, having a rheumatologist on the study team provides someone mentors can reach out to for rapid clinical feedback. When we encounter serious psychosocial (abuse, neglect, suicidal thoughts) or medical issues that need to be referred, [name] will be the primary contact for less urgent issues and responsible for linking participants to appropriate services. [name] will ensure that more urgent referrals are addressed within the MUSC hospital system. Participants requiring medical or other professional intervention for study-related events will be provided with appropriate and timely medical guidance by the Pl. If adverse events occur during the conduct of this study, they will be reported to the MUSC IRB in accordance with Section 4.7 - Unanticipated Problems and Adverse Events Policy and Procedures.

To protect against the potential risk of loss of confidentiality and/or breach of privacy, data will be compiled using codes in lieu of personal identifiers. Access to study data will be limited to research personnel. Development of and security oversight for the electronic database for this study will be performed by the PI and study statistician. Paper documents pertaining to this study will be stored in locked file cabinets and electronic data will be entered into secure, password-protected databases developed for this study by the research assistants. The PI will perform periodic review of the data entry

process to ensure accuracy of recording. When study results are published or presented, only aggregate reports of the results will be used and participants' identity will not be revealed. A file of name, contact address, telephone number, and other research identification numbers will be stored separately on paper and on computer, for purposes of audit by the MUSC IRB, if necessary. To further ensure confidentiality, participants will be provided with a web-enabled phone and calling/texting/data plan for the duration of the study for mentoring and support group interactions so that personal phones are not used.

In the event of negative interactions between mentor and mentee, the following steps will be taken:

- 1. The PI will communicate with mentees and mentors on a bi-weekly basis to assess calling patterns, content of calls, any other interactions between mentor and mentee, and any concerns either may have.
- 2. Mentees and mentors will be encouraged to contact the PI at any time if they run into a difficult situation with a mentee. If during such communication, mentee or mentor reports that they believe that their mentee/mentor may be depressed, homeless/displaced, suicidal, has broken confidentiality, is repeatedly asking for medical advice, prying too much into their personal life, or that they are simply not connecting with who they have been paired with, the PI will meet with each party individually to discuss, troubleshoot, and develop solutions or direct to services, when applicable.
- 3. If the mentor/mentee does not resolve the issue successfully on their own (with the exception of issues of suicidality, depression, and homelessness, which they are instructed to turn over to the PI to handle/address), the PI will meet with the pair together to discuss, troubleshoot, and develop solutions.
- 4. If the mentor and mentee agree to continue, but report that issues can/have not been resolved, the PI will reassign to a different mentee/mentor, making every effort to match as closely as they were originally paired.
- 5. If complaints persist about a specific mentor or mentee that contradict study procedures (e.g., breaking confidentiality, not adhering to intervention format), that participant could be asked to leave the study.

Mid-point Analyses for the protection of participants: In an effort to protect both mentors and mentees from potential deleterious effects of mentoring, a mid-point (interim) analysis will be undertaken to assess safety using 3-month post-intervention data. If mentored participants have worsened beyond a threshold, we will stop the trial for ethical concerns. For instance, if the lower confidence limits based on 95% confidence interval at the midpoint, for any one of the variables, namely depression, anxiety, and/or disease activity, is larger than 50% compared with their baseline measure, the trial will be terminated. Similarly, mentors will be monitored for depression, anxiety, and disease activity and if a worsening trajectory is observed at mid-point analyses, they will be removed from the study.

The overarching aims of this pilot project is to test the efficacy of a peer mentoring intervention in three hundred (300) African American women with systemic lupus erythematosus (SLE) (60 mentors and 300 mentees). Our rationale is that peers who have experience in managing their lupus may be in a better position to share knowledge and experience with which others may often not be able to relate. This can establish trust and in turn decrease disparities in health care outcomes. The proposed study if successful will lead to mentees' improved health-related quality of life, self-management, and disease activity. The project is innovative because it will be the first study of its kind in this field to test peer mentorship as an alternative strategy to improve outcomes in this population. Given the success of the peer mentoring approach in other chronic conditions that disproportionately impact minorities, and its responsiveness to the needs of this unique population, this intervention could result in health improvements that have not been attainable with other interventions. This would significantly reduce disparities and have considerable public health impact.

With assistance from appropriate staff, the Principal Investigator (PI) will serve as the safety monitor for the study. The functions of the SM/PI will include: 1) provide scientific oversight; 2) review all adverse effects or complications related to the study; 3) monitor accrual; 4) generate summary reports relating to compliance with protocol requirements; and 5) guide resource allocation. The PI will review and

recommend appropriate action regarding adverse events and other safety issues. The PI will also be responsible for submitting all reports to NINR.

Study procedures and participants will be monitored throughout the course of the project to ensure patient safety and minimal risk. Study coordinators will monitor study participants at consent, all data collection encounters, and during intervention activities for any discomfort, satisfaction with study participation, and for any questions or concerns participants may have. Frequency will be determined by the rate of recruitment and enrollment. It is the study coordinator's responsibility to ensure that all returned forms are complete, intact, and transmitted to the PI and Biostatistician, as appropriate. The PI will maintain at least weekly communication with coordinators and other study team members for progress, updates, and any concerns. If a concern is raised, it will be addressed immediately. The PI will coordinate communication and/or meet with necessary parties to resolve the matter and take appropriate action (e.g., notify IRB and/or NINR, notify participant(s), amend approved IRB protocol, etc.).

On a daily basis, the PI and Biostatistician will ensure the security of all data files. At critical data collection junctures (baseline, mid-intervention, immediately post-intervention and 6 months postintervention), the PI will review the data set to ensure de-identification prior to analysis. It is the Biostatistician's responsibility to enter, manage and analyze data, and transmit outputs and summarized results to the PI, as appropriate. On a bi-weekly basis (according to the schedule of intervention and support group sessions), the PI will monitor mentor and mentee reports of their activities and communications to ensure that they are safe and to detect any unexpected adverse events and report any concerns to the institutional IRB. Summaries of adverse events reports or patient safety concerns reported to the IRB will be made to NINR in the annual progress report unless the nature of a particular event is such that it warrants immediate reporting. If any adverse events or serious adverse events occur during the conduct of this study, they will be reported to the MUSC IRB in accordance with Section 4.7 -Unanticipated Problems and Adverse Events Policy and Procedures. The timeframe for collecting adverse events will be from the time of enrollment to last follow-up. Adverse events will be collected during each follow-up phone call or meeting by prompting participants to let the study coordinator or other research team member know if they have experienced any adverse events. In addition, should events be reported in-between follow-up calls, those will be recorded immediately. The study coordinator will inform the principal investigator of SAE and AEs by phone or secure email communication. The principal investigator will, in turn, inform the IRB immediately by updating the study record in the Health Sciences South Carolina (HSSC) eIRB system. As the PI receives notification of any study-associated adverse event, that information will be immediately shared with the overseeing IRB. Notification of an adverse or serious adverse event may be provided by the participant, MUSC study coordinator, etc. All Serious Adverse Events (SAE's) will be reported to NINR within 48 hours of the Principal Investigator becoming aware of the event.

In an effort to protect both mentors and mentees from potential deleterious effects of mentoring, a midpoint (interim) analysis will be undertaken to assess safety using 3-month post-intervention data. If mentored participants have worsened beyond a threshold, we will stop the trial for ethical concerns. For instance, if the lower confidence limits based on 95% confidence interval at the midpoint, for any one of the variables, namely depression, anxiety, and/or disease activity, is larger than 50% compared with their baseline measure, the trial will be terminated. Similarly, mentors will be monitored for depression, anxiety, and disease activity and if a worsening trajectory is observed at mid-point analyses, they will be removed from the study.

The PI will document all study activities and communications and generate formal quarterly, annual and final reports that will be disseminated to the study team and NINR program officer. At least quarterly meetings will be held with the entire study team, for regular review of research progress and for general project oversight and guidance.

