## Primary Outcomes for Aim 1 will include:

Quality of Life: The LUP-QOL incorporates the Medical Outcomes Study (MOS) Short Form 36 Health Survey (SF-36) and the Functional Assessment of Chronic Illness Therapy-Fatigue (FACIT-F), which are reliable and valid instruments that are frequently used in quality of life studies of persons with lupus.[120,121] Self-Management: The Patient Activation Measure (PAM)[122,123] assesses an individual's knowledge, skill, and confidence for managing their health and healthcare. Individuals who measure high on this assessment typically understand the importance of taking a pro-active role in managing their health and have the skills and confidence to do so.

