Power and Sample Size Justification: The sample size calculation and power analyses are based on the primary outcome of change in HRQOL between baseline and 12 months post intervention. The minimum sample size was based on detecting a clinically meaningful difference of 0.35 standard deviation units (medium effect) based on prior studies.[87,93,139-143] Essentially, this is equivalent to testing the interaction between time and group. Assuming 3 measurement time points, level of significance p=0.05, two-tailed comparison, correlation between pairs of measurements within participants (interclass correlation) no larger than p=0.6, compound symmetry covariance structure, we estimate that 123 participants per group (total n=246) are needed to detect, with 80% power, a standardized effect size of at least 0.35sd. This sample size includes a 20% inflation for attrition at 12 months. This effect size is robust enough to provide sufficient power for the outcomes listed under aims 1 and 2 and is consistent with data from our pilot study of 20 mentees and 7 mentors (see preliminary data). The pre-post differences in the outcomes (such as overall social support, positive social interaction, tangible support, vitality, emotional support, social functioning, general health, coping, etc), ranged from 0.35 to 0.88 standard deviation units. Although these calculations account for within patient clustering through the intera-class correlation mentioned above, clustering within mentors and mentees are assumed to have minimal intra-class correlation based on pilot data, especially since the cluster sizes would be at most 3 at a given wave. However, a multi-level model will be used in the analysis to verify this. Since the effect size planned is conservative, if the clustering leads to higher intra-class correlation, we would still be able to detect meaningful differences. We will also consider including mentor as a fixed effect in the model.

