AIM 1: Determine the efficacy of a peer mentorship intervention in African American women with SLE on disease self-management and HRQOL. Analyses for Aim 1 will focus on estimation of efficacy as determined by: (a) change in quality of life; and (b) change in self-management. Estimates of effect sizes for outcome variables will be reported as point estimates (mean differences between pre-post measures. as appropriate) and interval estimates (95% CI) with two-sided p-vales denoting statistical significance to provide an indication of the presence of a clinically important treatment effect. [145,146] A p-value of 0.05 will be considered to be statistically significant. After studying the distributions of baseline characteristics. we will use a generalized linear mixed model regression model to determine if the intervention will produce a greater change in the main outcomes from baseline. This model will include time, treatment (along with their interaction), and covariates (including the amount of intervention received, demographic factors, medications, coping, depression, stress, anxiety, health literacy, trust, and social support) as fixed-effects. Using the amount of intervention, which is measured as an aggregate number of sessions completed or hours of interaction as a covariate would allow us to study the dose response. In the generalized linear mixed model (GLMM), we will use different link functions depending on the assumed distribution of the response variable. For binary outcomes, we will use logit link and for count outcomes we will use log link under a poisson or negative binomial distribution. For example, for the a given quality of life variable, HRQOL measured at baseline, month 3 and month 6, we will include intervention group, time, and time X intervention as the primary independent variables in the basic (unadjusted) model, and covariates that are not balanced at randomization (or a propensity score based on these covariates) will be added in the subsequent (adjusted) model to adjust for the possible confounding effect of these variables. Unadjusted and covariate-adjusted least squares means for each outcome variable will be compared at the primary time point (month 12) and at intermediate secondary time point (month 6) using appropriate model contrasts and the Tukey-Kramer adjustment for multiple comparisons for the secondary time points. These contrast comparisons, along with corresponding 95% CI, will provide estimates of the difference in outcome means (effect sizes) for the hypothesized comparisons.

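### Aim 1 has two primary outcomes, each judged at 0.05, with no rule for combining them, while the sample size rests on HRQOL alone

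*Combined protocol and SAP*

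**What the plan says.** The subsection headed "Primary Outcomes for Aim 1 will include" lists two measures: LUP-QOL for quality of life and PAM for self-management. Hypothesis 1, in the opening statement of aims, names the same two instruments at 12 months after randomization. The same subsection describes LUP-QOL as incorporating the SF-36 and the FACIT-F. It names no total or domain score as the primary one.

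Under AIM 1 in the Overview of Statistical Analysis Plan, efficacy is judged on change in quality of life and change in self-management. Means for each outcome variable are compared at month 12, the primary time point. The level is given once: "A p-value of 0.05 will be considered to be statistically significant". The only multiplicity provision is "the Tukey-Kramer adjustment for multiple comparisons for the secondary time points".

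The Power and Sample Size Justification states: "The sample size calculation and power analyses are based on the primary outcome of change in HRQOL". It uses the full two-sided 0.05 for that one outcome. It then asserts, without a calculation, that power is sufficient for the other outcomes of Aims 1 and 2.

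**The concern.** With two primary outcomes, a plan needs a rule for what counts as success. The usual choices are one primary with the other tested in sequence, a split of alpha, or a requirement that both succeed. Each has its own consequence for error or power, and this plan chooses none of them.

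The Tukey-Kramer adjustment does not fill the gap, because it works across secondary time points and not across outcomes. A reader of the final report could not tell whether significance on PAM alone, with LUP-QOL missing, would be a confirmed effect. The trial's stated immediate goal is to determine efficacy, so the claim could rest on whichever of the two outcomes crosses 0.05. The unnamed LUP-QOL score leaves a further choice open.

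**Working it through.** **Inputs**
- From the Power and Sample Size Justification: "Assuming 3 measurement time points, level of significance p=0.05, two-tailed comparison"; within-participant correlation "no larger than p=0.6, compound symmetry covariance structure"; and 123 per group, which "are needed to detect, with 80% power, a standardized effect size of at least 0.35sd", including 20% for attrition.
- From B4b Study Overview: planned enrolment of 150 per arm.
- From the feasibility-of-recruitment text: 10% attrition in the pilot.
- Assumed: the correlation r between the LUP-QOL and PAM test statistics, which the documents do not give. The range shown is 0 to 0.9. Both true effects are set at exactly 0.35 SD, and PAM is given the same within-participant correlation as HRQOL.

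**1. Reproduce the plan's sample size**

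Under compound symmetry at 0.6, the variance of a change score is 2(1 − 0.6) = 0.8 in squared SD units.

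n per arm = 2 × 0.8 × ((1.960 + 0.842)/0.35)² = 102.5. Multiplying by 1.2 gives 123.0, which matches the stated 123.

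Section B4c gives the same 123 with a correlation of 0.7 and AR(1). The figures below use the 0.6 compound-symmetry inputs.

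**2. Power for one outcome at 0.05**

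Power = Φ(0.35/√(0.8 × 2/n) − 1.960)

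| Evaluable per arm | Source | Power |
|---|---|---|
| 98.4 | 123 less 20% | 78.4% |
| 103 | 102.5 rounded up | 80.2% |
| 120 | 150 less 20% | 85.8% |

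The 78.4% arises because attrition was allowed for by multiplying by 1.2 and not by dividing by 0.8.

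**3. If either outcome suffices**

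Familywise error = 1 − P(|Z₁| < 1.96 and |Z₂| < 1.96), with no true effect on either outcome.

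- r = 0: 1 − 0.95² = 9.75%
- r = 0.5: 9.1%
- r = 0.7: 8.3%
- r = 0.9: 7.0%

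These figures do not depend on n, so enrolling 300 does not reduce them.

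**4. If both must succeed**

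Alpha is not inflated. Joint power is the bivariate normal probability that both statistics exceed 1.96:

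| Evaluable per arm | r = 0 | r = 0.5 | r = 0.7 | r = 0.9 |
|---|---|---|---|---|
| 98.4 | 61% | 67% | 69% | 73% |
| 103 | 64% | 69% | 72% | 75% |
| 120 | 74% | 77% | 79% | 82% |
| 135 (150 less 10%) | 80% | 83% | 84% | 86% |

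**5. If alpha is split equally (0.025 each)**

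n = 2 × 0.8 × ((2.241 + 0.842)/0.35)² ≈ 124 evaluable per arm for 80% power per outcome. Power per outcome is 69% at 98.4 and 78.5% at 120.

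**The case against.** A reader might infer that a stated property of the design fails whichever rule is meant. The documents do not support that. They state no familywise error rate and no joint power. The 80% is stated for HRQOL alone, and step 2 shows that it essentially holds. What is missing is a decision rule.

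The power shortfall is also not certain. Hypothesis 1 joins the two outcomes with a conjunction, so requiring both is a natural reading, and on that reading alpha is safe. The shortfall is firm at the stated total of 246. At the planned 300 it is modest with 20% attrition, disappears there if the outcomes are very highly correlated, and is absent with the pilot's 10% attrition. The plan also describes 0.35 SD as a minimum effect. This part of the objection stands.

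A reader might also infer that any quality-of-life score may serve as primary, each tested at 0.05. The phrase that suggests this belongs to a worked example of model terms, and LUP-QOL is the named instrument. No count of primary scores is given, so error rates for many sub-scores would have no basis in the documents. The supported point is narrower: no LUP-QOL score is fixed as primary.

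Finally, the power section might be read as already choosing that score. It says only HRQOL.

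None of this supplies the missing rule. Nothing in the plan prevents an efficacy claim on one outcome alone, and extra enrolment does not address that.

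**Conclusion.** The point holds as a gap in the success criterion for Aim 1. There are two primary outcomes at month 12, each judged at 0.05, with no rule linking them and a sample size built on one.

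The consequence depends on the rule that is eventually applied. An either-outcome claim carries about 7 to 10% familywise error. A both-required claim keeps 5% but has joint power of 61 to 73% at the stated sample size and 74 to 82% at planned enrolment, each after 20% attrition. These ranges rest on assumed between-outcome correlations of 0 to 0.9, and the joint-power figures also on a true effect of 0.35 SD for both outcomes. The HRQOL power statement itself is not in dispute.

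**What to change.** In the Aim 1 primary-outcomes subsection and the AIM 1 analysis text:

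1. Name one prespecified LUP-QOL score, compared between arms at month 12, as the first primary test at two-sided 0.05. This is consistent with sizing the trial on HRQOL.
2. Test PAM at month 12 at two-sided 0.05 only if the first test is significant.
3. Report all other HRQOL scores as secondary, with confidence intervals.

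This controls the error across the two primary tests at 5% and takes no power from HRQOL. It needs only a change of wording. The cost is that no confirmatory PAM claim can be made if LUP-QOL misses, which ranks PAM below an outcome that the plan now lists beside it.

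If the sponsor wants equal primaries, a Bonferroni split at 0.025 each is workable. It gives about 78.5% power per outcome at 120 evaluable per arm, and the protocol should then state that figure. If both outcomes must succeed, the plan should say so and give the joint power with its assumed correlation. The Tukey-Kramer provision for secondary time points can stay, since removing it is not needed to cure this gap.
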